8.4.2.3 Local and Systemic reactions, Hypersensitivity and Anaphylaxis reaction to Injection

All adverse events reported as related to sub-cutaneous injection of study treatment will be presented as by-subject listing and summarized by System Organ Class (SOC) and Preferred term (PT). The list of SOC and PT to be used for this purpose are presented in Section 10.1.

8.4.2.4 Risk factors for injection site reactions

The available data will be reviewed to identify any potential risk factors and risk groups for injection site reactions.

The risk factors more commonly include the skin's response to the needle or the medicine. An allergic reaction to the medicine or an infection at the injection site.

Possible risk factors that can be analyzed include:

- Dose
- Frequency of Injection
- History of injection site reactions
- Patient demographics

8.4.2.5 Impact of injection site reactions on patient outcomes (e.g., leronlimab discontinuation, additional treatment required or preventative measures)

Any impact of injection site reactions on patient outcomes (e.g., leronlimab interruption, discontinuation, additional treatment or preventative measures required) will be presented

8.4.3 Clinical Laboratory Evaluations

All results of laboratory evaluations will be presented as by-subject listings.

8.4.3.1 Laboratory Values over Time

Summary statistics of raw data and change from baseline values for each laboratory parameter will be presented by treatment group and time point. Data will be summarized as appropriate for the variable type.

For change from baseline summaries, subjects with an undefined change from baseline, because of missing data, will be excluded.

8.4.3.2 Individual Patient Changes

Laboratory data will be classified into grades according to DAIDS toxicity grading. A severity grade of 0 will be assigned when the value is within normal limits.

The following summaries will be produced for the hematology and biochemistry laboratory data (by laboratory parameter):

- Shift tables using DAIDS grades to compare baseline to the worst post-baseline value will be produced for hematology and biochemistry laboratory parameters with DAIDS grades
- Shift tables using Low/High/Normal relative to the laboratory reference ranges to compare baseline to the worst post-baseline value will be produced for hematology and biochemistry laboratory parameters without DAIDS grades

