- d. The occurrence in any subject of a life-threatening SAE whose causal relationship to leronlimab (PRO 140) is judged to be probable or definite
- e. The occurrence of one or more non-life-threatening SAEs whose causal relationship to leronlimab (PRO 140) is judged to be definite
- f. The occurrence, in one or more subjects, of Grade 4 laboratory abnormalities, judged to be probably or definitely related to receipt of leronlimab (PRO 140)
- g. The occurrence of hematologic and non-hematological adverse events, judged to be possibly, probably or definitely related to receipt of leronlimab (PRO 140) based on previous clinical experience and that are of CTCAE Grade 3 or greater severity. Permissible exceptions to this rule include Grade 3 fatigue of less than one week duration, and Grade 3 nausea, vomiting, and diarrhea that resolve within 48 hours following institution of appropriate supportive care.
- h. Hy's law
- i. Neutropenic fever
- j. Grade 4+ neutropenia or thrombocytopenia >7 days
- k. Grade 3+ thrombocytopenia with bleeding
- l. Grade 3+ electrolyte abnormality that lasts >72 hours, unless the patient has clinical symptoms, in which case all grade 3+ electrolyte abnormality regardless of duration should count as a DLT. Grade 3+ amylase or lipase elevation NOT associated with symptoms or clinical manifestations of pancreatitis does not need to be counted as a DLT
- m. For patients with hepatic metastases, AST or ALT >8xULN or AST or ALT >5x ULN for ≥ 14 days

If any of the SAEs or DLTs outlined above have occurred, the Data Safety Monitoring Board (DSMB) will conduct an independent review of the data and make a final decision for dose escalation to the next cohort.

The dosing regimen for each cohort is as follows:

- Cohort A: 350 mg leronlimab (PRO 140) SC weekly + AUC 5 Carboplatin every 3 weeks
- Cohort B: 525 mg leronlimab (PRO 140) SC weekly + AUC 5 Carboplatin every 3 weeks
- Cohort C: 700 mg leronlimab (PRO 140) SC weekly + AUC 5 Carboplatin every 3 weeks

Leronlimab (PRO 140) is administered as subcutaneous injection in the abdomen weekly. A total of 350 mg, 525 mg, or 700 mg (175 mg/mL) is delivered as two injections on opposite sides of the abdomen. The 350 mg dose will be delivered as two injections of 1 mL each, 525 mg dose will be delivered as two injections of 1.5 mL each and 700 mg dose will be delivered as two injections of 2 mL each.

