6.2.13. Carboplatin - Toxicity Management & Dose Delays/Modifications

The dose interruption, reduction, and permanent discontinuation for any toxicity are described below.

Dose interruption: Refer to table below. Recovery to acceptable levels must occur to allow carboplatin continuation.

Table 6-4: Carboplatin Dose Modification and Management

Toxicity	Grade/Description	Carboplatin
Hematologic Toxicities		
Thrombocytopenia	Grade 1	Maintain dose level.
	Grade 2	Hold dose & follow CBC weekly. Once \leq Grade 1 (platelets \geq 75,000/mm ³), resume at same dose.
	Grade 3	Dose reduction to AUC 4
	Grade 4	Permanently discontinue Carboplatin
Neutropenia	Grade 1 , 2 or 3 without fever	Maintain dose level.
	Grade 3 w/ fever or Grade 4	1st occurrence: Hold dose & follow CBC weekly. Once resolved to $> 1.0 \times 10^9/L$ (if neutropenia was the only toxicity noted), resume at same dose. If other toxicity was noted, resume with AUC 4. 2nd occurrence: Discontinue Carboplatin
Non-Hematologic Toxicities		
Allergic reaction or hypersensitivity	\leq Grade 3	Hold dose until resolved to \leq Grade 1 & then resume at same dose level.
	Grade 4	Permanently discontinue Carboplatin

Toxicity	Grade/Description	Carboplatin
Infection	Grade 1 or 2	Hold dose until systemic treatment for infection is complete. If no neutropenia, resume at same dose level. If neutropenic, follow instructions above (hematologic section). If no resolution after > 3 weeks: permanently discontinue Carboplatin
	Grade 3	Discontinue Carboplatin
Herpes zoster or simplex	Any grade	Hold dose until lesions are dry & then resume at same dose level.
Neuropathy	Grade 2 w/pain or Grade 3	Hold dose until resolved to \leq Grade 2 or baseline then resume at AUC 4. May continue on single-agent leronlimab (PRO 140) (per treating investigator's discretion)
	Grade 4	Permanently discontinue Carboplatin
Renal dysfunction	CrCl \leq 15 mL/min	Hold dose until CrCl $>$ 15 mL/min & then resume.

Note: Patients who discontinue carboplatin for any reason will be allowed to continue to receive leronlimab (PRO 140) per treating investigator's discretion. In such cases, patients will be re-consented so that they are appropriately informed of other treatment options that have demonstrated improvement in clinical outcomes.

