7.10 TOXICITY ASSESSMENT

Any subject who receives at least one dose of study therapy will be evaluable for toxicity endpoints. Each subject will be assessed for the development of toxicity according to the timeframe referenced in the Schedule of Events table. Toxicity will be assessed according to CTCAE v 5.0 criteria. Refer to [Section 3](#) for the assessment criteria for dose limiting toxicity under Phase Ib of the study. Also

refer to [Table 6-3](#) and [Table 6-4](#) for the dose modification and management of leronlimab (PRO 140) and carboplatin for any toxicity.

All subjects will be followed for adverse events for 30 days after last dose of leronlimab (PRO 140) and carboplatin, or until the subject starts a new treatment, whichever occurs first.

Subjects who discontinue treatment for unacceptable adverse event(s) will be followed until resolution or stabilization of the adverse event (i.e. the grade is not changing). If a subject stops treatment due to unacceptable adverse event(s) but has not demonstrated disease progression, then the subject will be followed with imaging studies every 9 weeks until the time of progression radiographically according to RECIST v1.1 criteria.

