2.5 Safety Assessments

Safety will be assessed by close monitoring and timely assessment of adverse events (AEs), laboratory parameters (blood tests, urinalysis), vital signs (blood pressure, heart rate), subject's medical condition (physical examination including weight), general well-being and activities of daily life (Eastern Cooperative Oncology Group (ECOG) performance status). Each subject will be regularly assessed in each cycle for potential AEs and disease related signs and symptoms. The CTCAE v5.0 will be used to grade toxicities/AEs.

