4. INTERIM ANALYSIS/DSMB

No interim analysis (IA) will be performed for efficacy. There will be a safety review, once all three (or six) subjects from each cohort complete the DLT evaluation period (defined as cycle 1 or the first 21 days of treatment).

The Sponsor's Medical Monitor, CRO Medical Monitor and study investigators must be satisfied with data obtained in Cohort A before allowing subsequent enrollment of Cohort B. Likewise, they

must be satisfied with data obtained in Cohort B before allowing subsequent enrollment in Cohort C.

In addition, should any of the following events occur in any cohort during the DLT evaluation period, the Data Safety Monitoring Board (DSMB) will meet to review available study data and make a final decision for dose escalation to the next cohort:

- a. Death in any subject in which the cause of death is judged to be possibly, probably or definitely related to leronlimab (PRO 140)
- b. The occurrence in any subject of an anaphylactic reaction to leronlimab (PRO 140)
- c. The occurrence in any subject of a severe local injection site reaction (Grade 3 which is not resolved or recurs; or Grade 4) that precludes administration of consecutive leronlimab (PRO 140) doses.
- d. The occurrence in any subject of a life-threatening SAE whose causal relationship to leronlimab (PRO 140) is judged to be probable or definite
- e. The occurrence of one or more non-life-threatening SAEs whose causal relationship to leronlimab (PRO 140) is judged to be definite
- f. The occurrence, in one or more subjects, of Grade 4 laboratory abnormalities, judged to be probably or definitely related to receipt of leronlimab (PRO 140)
- g. The occurrence of hematologic and non-hematological adverse events, judged to be possibly, probably or definitely related to receipt of leronlimab (PRO 140) based on previous clinical experience and that are of CTCAE Grade 3 or greater severity. Permissible exceptions to this rule include Grade 3 fatigue of less than one week duration, and Grade 3 nausea, vomiting, and diarrhea that resolve within 48 hours following institution of appropriate supportive care.
- h. Hy's law
- i. Neutropenic fever
- j. Grade 4+ neutropenia or thrombocytopenia >7 days
- k. Grade 3+ thrombocytopenia with bleeding

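### SAP 8.4.3.2 grades laboratory values on DAIDS although the protocol and SAP 2.5 set CTCAE v5.0, so the laboratory shift tables cannot be relied on to correspond to the grades used for DLTs, dose modification and AE severity

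*SAP*

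**What the plan says.** The SAP uses two toxicity scales.

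- SAP 2.5 sets the general rule: "The CTCAE v5.0 will be used to grade toxicities/AEs".
- SAP 8.4.3.2 departs from it for laboratory data: "Laboratory data will be classified into grades according to DAIDS toxicity grading". It adds: "Shift tables using DAIDS grades to compare baseline to the worst post-baseline value will be produced". Haematology and biochemistry parameters that have no DAIDS grade get Low/High/Normal shift tables against the reference ranges.
- SAP 8.4.2.1 also uses a DAIDS-based table, for injection-site reactions.

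The protocol uses one scale. Section 7.10 reads: "Toxicity will be assessed according to CTCAE v 5.0 criteria". Sections 8.7.3.2 (safety analyses) and 9.2.2 (AE intensity) also name CTCAE v5.0, and 9.2.6 names it for injection-site reactions. I found no mention of DAIDS in the protocol.

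**The concern.** Marrow suppression is the toxicity of most interest here. Protocol 1.3.2 describes it as dose-limiting for carboplatin and expects leronlimab to add no major toxicity. Graded blood counts are a natural check on that expectation.

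The shift tables matter because of what the AE tables leave out. Under protocol 7.11, a laboratory abnormality becomes an AE only if the investigator judges it clinically significant. Low counts not so judged appear in no AE table. Their only graded summary is the shift table, on a scale that the rest of the trial does not use. A reader who sees a Grade 3 or 4 shift in platelets or neutrophils could not safely set it beside the DLT criteria, the carboplatin table or the AE severity tables.

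**Working it through.** No arithmetic decides this point. The check compares every statement about a grading scale.

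**1. Which scale governs the grades the trial acts on**

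- DLT item g (protocol 3, repeated in SAP 4) names the scale: events "that are of CTCAE Grade 3 or greater severity".
- Items f, j, k and l rest on grades without naming a scale. Item j, for example, is "Grade 4+ neutropenia or thrombocytopenia >7 days". Item m uses multiples of the upper limit of normal and needs no scale.
- Table 6-4 acts on grades, also without naming a scale. For Grade 3 thrombocytopenia its entry is "Dose reduction to AUC 4".
- Protocol 7.10 supplies the link. It sets CTCAE v5.0, then points to Section 3 for the DLT criteria and to Tables 6-3 and 6-4 "for the dose modification and management of leronlimab (PRO 140) and carboplatin for any toxicity".

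CTCAE is therefore explicit for item g and inferred through 7.10 for items f, j, k, l and Table 6-4. The inference is sound, because the protocol offers no other toxicity scale.

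**2. Which laboratory outputs carry a grade**

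- SAP 8.4.3: listings of all results, ungraded.
- SAP 8.4.3.1: raw values and change from baseline, ungraded.
- SAP 8.4.3.2: shift from baseline to worst post-baseline value, DAIDS grades.
- SAP 8.4.3.3: shift in the investigator's interpretation (normal, abnormal not clinically significant, abnormal clinically significant), no toxicity grade.
- SAP 8.4.3.4: listing of abnormalities recorded as AEs.
- SAP 8.4.1: AE tables by severity grade, CTCAE v5.0 under SAP 2.5, limited to results that became AEs.

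Only 8.4.3.2 grades laboratory results regardless of the clinical-significance judgement.

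**3. Whether the two scales can be assumed equal**

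Neither document prints laboratory cut-points for DAIDS, and CTCAE is given only as general guidelines and a link. The one laboratory grade boundary printed is in Table 6-4, where platelets of at least 75,000/mm³ count as Grade 1 or less. There is nothing on the DAIDS side to set against it.

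One comparison outside the laboratory is possible. Protocol Table 9-1 (CTCAE general guidelines) lists an indication for hospitalization under Grade 3. SAP Table 8-1 (DAIDS-based) lists it under Grade 4 for injection-site pain. Equal grade numbers therefore cannot be presumed to mean equal severity. This says nothing about any particular laboratory cut-point.

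**4. Size**

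Each shift table uses one baseline grade and one worst post-baseline grade per subject. With up to 18 subjects in Phase Ib and 30 in Phase II, that is at most 18 + 30 = 48 worst grades per parameter. The number that would change between scales runs from 0, where cut-points coincide, up to every worst value lying between two differing cut-points. The documents do not allow it to be narrowed further.

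**The case against.** The strongest case against runs as follows.

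- **The harm is not demonstrated.** Without the cut-points, nobody can show from these documents that a single platelet or neutrophil value would change grade. This stands. A reader might infer that the tables will disagree, or that the trial will report two rates of Grade 3–4 cytopenia. The documents do not support that. They support only the statement that agreement cannot be relied on.
- **The outputs would differ on one scale too.** AE tables hold only clinically significant results. DLTs are confined to Cycle 1, and several items add relatedness, duration or bleeding. The SAP names no DLT table, only a descriptive MTD summary in 8.2.1. This also stands, so a common scale should not be presented as making the tables agree one for one. It would remove an avoidable further source of difference.
- **No decision depends on these tables.** DLT calls, escalation and AE intensity follow the protocol, and PFS and the MTD are untouched. A reader might infer that dosing or escalation is compromised. Nothing in the documents suggests it.
- **The tables are an extra, and raw values are listed.** Protocol 8.7.3.2 asks only for listings and continuous summaries of laboratory data, and anyone can regrade later from the listings. True, but once the SAP specifies a graded table its scale should be the trial's own or be justified. Later regrading would also be a choice made after seeing the data.
- **The scale may be suitable.** A reader might infer that DAIDS is invalid here because known HIV-positive patients are excluded. That does not follow, since the title quoted in SAP 8.4.2.1 refers to adult and paediatric adverse events generally. The objection to DAIDS is inconsistency and lack of justification.

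**Conclusion.** The point holds as an inconsistency in the analysis plan. SAP 8.4.3.2 conflicts with SAP 2.5 and with the protocol's CTCAE v5.0 rule, and no other text reconciles them. Its consequence is limited to interpretation: the one graded summary of haematology and biochemistry that does not depend on investigator judgement cannot be read with confidence against the rest of the safety reporting.

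It affects the worst grade, not each cycle's value. The conclusion assumes that protocol 7.10 governs the DLT items and Table 6-4 entries that name no scale. It assumes nothing about where the DAIDS and CTCAE laboratory cut-points lie. This should be corrected before database lock, but it does not threaten the primary results.

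**What to change.** In SAP 8.4.3.2, replace DAIDS with CTCAE v5.0 in the grading sentence and in both bullets. Keep the Low/Normal/High shift tables, and apply them to parameters without numeric CTCAE grades. If the sponsor has a reason to keep DAIDS, the SAP should give that reason and the version, and add CTCAE v5.0 shift tables alongside.

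Reconcile the injection-site grading in SAP 8.4.2.1 with the protocol's CTCAE v5.0 in the same revision, because correcting one section leaves the other unchanged.

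The laboratory change costs SAP wording and one grading look-up in programming. It needs no new data and changes no DLT or dose-modification rule.

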8.4.3.3 Individual Subject Changes on Interpretation

Shift tables will be presented for the investigator lab interpretation (i.e., Normal, Abnormal (not clinically significant) and Abnormal (clinically significant)) with counts and percentages of subjects, by treatment group, for shift (change) from baseline, using the normal ranges.

8.4.3.4 Individual Clinically Significant Abnormalities

Clinically significant laboratory abnormalities (i.e., those laboratory abnormalities recorded as AEs) will be listed.

8.4.4 Vital Signs

Vital sign assessments are performed in order to characterize basic body function. The parameters collected in this study are: systolic BP (mmHg), diastolic BP (mmHg), temperature (0C), heart rate (bpm), respiratory rate (rpm).

8.4.4.1 Clinically notable elevated values

- Systolic BP: \geq 160 mmHg and an increase \geq 20 mmHg from baseline
- Diastolic BP: ≥ 100 mmHg and an increase ≥ 15 mmHg from baseline.
- Body temperature: ≥ 39.1 °C
- Heart rate: ≥ 120 bpm with increase from baseline of ≥ 15 bpm
- Respiration rate: ≥ 24 breaths per minute with increase from baseline of ≥ 6 breaths per

minute

8.4.4.2 Clinically notable below normal values

• Systolic BP: \leq 90 mmHg and a decrease \geq 20 mmHg from baseline

• Diastolic BP: ≤ 50 mmHg and a decrease ≥ 15 mmHg from baseline

• Body temperature: ≤ 35°C

• Heart rate: ≤ 50 bpm with decrease from baseline of ≥ 15 bpm

 Respiration rate: < 8 breaths per minute with decrease from baseline of ≥ 6 breaths per minute

Number and percentage of patients with at least one post-baseline vital sign abnormality (in both directions, i.e. both elevated and below normal values) will be summarized by treatment group.

8.4.5 Electrocardiogram (ECGs)

The ECG parameters include: ventricular rate (beats per minute), PR interval (msec), QRS interval (msec), QT interval (msec), and QTc interval (msec).

The number and percentage of patients having notable ECG interval values and newly occurring qualitative ECG abnormalities will be summarized by treatment group.

The following notable ECG interval values for each parameter will be presented as by-subject listing. Number and percentage of subjects with at least one occurrence of the below notable ECG changes will be summarized.

QT and QTc:

- (1) New >450 msec
- (2) New >480 msec
- (3) New >500 msec
- (4) Increase from baseline >30 msec
- (5) Increase from baseline >60 msec

Shift tables will also be presented for the categories of QT results (<=450, >450-480, >480-500, >500) with counts and percentages of subjects, for shift (change) from baseline.

PR:

(1) An increase >25% from baseline and PR >200 msec at any post-baseline assessment

QRS:

(1) An increase >25% from baseline and QRS >110 msec at any post-baseline assessment

Ventricular rate:

- (1) A decrease >25% from baseline and HR <50 bpm at any post-baseline assessment
- (2) An increase >25% from baseline and HR >100 bpm at any post-baseline assessment

In addition, individual subject changes will be identified through shift tables. Shift tables will be presented for the investigator ECG interpretation (i.e., Normal, Abnormal (not clinically significant) and Abnormal (clinically significant)) with counts and percentages of subjects, for shift (change) from baseline.

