7.9 ELECTROCARDIOGRAM (ECG)

A resting supine 12-lead ECG will be conducted at the Screening Visit (SV), at baseline (C1D1), and at End of Treatment (EOT) visit. A 12-lead EKG will be repeated during the study only if clinically indicated and at the discretion of the treating physician. The results will be evaluated by the Investigator. The following parameters will be recorded: ventricular rate (beats per minute), PR interval (msec), QRS interval (msec), QT interval (msec), and QTc interval (msec). Additionally, the Investigator will record the overall results of the ECG reading as either normal or abnormal, and as either not clinically significant or clinically significant. If abnormalities are observed, each will be recorded.

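### SAP 8.4.5 applies its QT limits to uncorrected QT as well as QTc, names only QT in the categorical shift table, and gives no correction formula

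*SAP*

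**What the plan says.** Protocol 7.9 has the site record ventricular rate, PR, QRS, "QT interval (msec), and QTc interval (msec"), and SAP 8.4.5 repeats that list, so QT and QTc are separate variables in both documents. Neither says how QTc is obtained.

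Under one joint heading for QT and QTc, SAP 8.4.5 sets five limits. Three are absolute, running from "1) New >450 msec" through 480 ms to "3) New >500 msec". Two are changes: "4) Increase from baseline >30 msec" and "5) Increase from baseline >60 msec". Values that meet them are listed by subject and also tabulated: "Number and percentage of subjects with at least one occurrence of the below notable ECG changes will be summarized".

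The next sentence provides the categorical table: "Shift tables will also be presented for the categories of QT results (<=450, >450-480, >480-500, >500"). It names QT and does not name QTc. A second ECG shift table, at the end of the section, uses the investigator's overall reading.

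Scheduled ECGs are few. Protocol 7.9 places them at screening, Cycle 1 Day 1 and end of treatment, with repeats only if clinically indicated.

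**The concern.** Uncorrected QT lengthens as the heart slows and shortens as it speeds up. A fixed limit on it therefore responds partly to heart rate and only partly to repolarisation. That matters in two ways.

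- **Flags from rate alone.** A patient whose rate is lower at a later visit can be counted as having a notable QT increase when QTc has not moved. The study has a single arm, so no control group would show how many such flags to expect as background.
- **The shift table.** If its variable is uncorrected QT, a patient with a long QTc and a fast rate appears in the lowest category.

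The missing formula affects the QTc rows too. If machines or sites use different corrections, the same tracing can fall in different categories.

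**Working it through.** The documents state no derived ECG figure, so there is nothing of theirs to reproduce. The check asks which SAP limits uncorrected QT crosses when QTc is held fixed, and the reverse.

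**Inputs.** The limits are from SAP 8.4.5. The correction is an assumption, since none is named; two common forms are shown as a range:

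- Fridericia: QTc = QT / (60/HR)^(1/3)
- Bazett: QTc = QT / (60/HR)^(1/2)

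**1. Slower rate, unchanged QTc.**

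- QTcF 420 ms at 90 bpm: QT = 420 × (60/90)^(1/3) = 366.9 ms. At 65 bpm: QT = 420 × (60/65)^(1/3) = 408.9 ms. The difference is +42 ms, above the 30 ms limit.
- QTc 400 ms, 80 to 60 bpm: +36.6 ms (Fridericia) or +53.6 ms (Bazett), above 30.
- QTc 400 ms, 100 to 60 bpm: +62.6 or +90.2 ms, above 60.
- QTc 400 ms, 70 to 60 bpm: +20.0 or +29.7 ms, no flag.

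**2. How often this would happen.** Assume constant QTcF 420 ms, one baseline and one later ECG, and independent normal heart rates with mean 75 and SD 8 to 12 bpm. None of these figures is in the documents.

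- QT at 75 bpm is 389.9 ms. The local slope is 389.9 / (3 × 75) = 1.73 ms per bpm.
- SD 8: the SD of the rate difference is 8 × √2 = 11.3 bpm, or 19.6 ms of QT. 30/19.6 = 1.53, an upper tail of about 6%.
- SD 12: 12 × √2 = 17.0 bpm, or 29.4 ms. 30/29.4 = 1.02, an upper tail of about 15%.
- Simulation with the exact formula gives about 7% to 16% above 30 ms and about 0.2% to 2.8% above 60 ms.
- In the 30 Phase II subjects that is 30 × 0.07 to 30 × 0.16, or about 2 to 5 flags above 30 ms with no drug effect.

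**3. The absolute limits are much less exposed to false flags.** With QTc 420 ms, uncorrected QT exceeds 450 ms only below about 49 bpm (Fridericia) or 52 bpm (Bazett). It can happen nearer the limit: 55 bpm with QT 460 ms gives QTcF 447 and QTcB 440, so raw QT is over 450 and QTc is not.

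**4. Long QTc in the lowest shift row.** The rate above which QT is 450 ms or less is 60 × (QTc/450)^3 for Fridericia and 60 × (QTc/450)^2 for Bazett.

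| QTc (ms) | Fridericia | Bazett |
|---|---|---|
| 481 | above 73 bpm | above 69 bpm |
| 501 | above 83 bpm | above 74 bpm |

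**5. Effect of the unnamed formula.** At 105 bpm with QT 385 ms, QTcF = 385 / 0.830 = 464 ms and QTcB = 385 / 0.756 = 509 ms. Raw QT is in the lowest row, while QTc is in the second row by one formula and the top row by the other.

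**The case against.** A reader might infer that the plan does not screen QTc at all, or that prolongation at a fast rate is filed as normal and hidden. The documents do not support that. The joint heading means all five limits also run on QTc. The 105 bpm example would, if new, be listed and counted as a notable QTc value under either formula. It could also meet the ventricular-rate criterion (above 100 bpm with a rise of more than 25%) and would be read by the investigator for the second shift table. The SAP does not call its lowest row normal.

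Three further points have force.

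- Under the joint heading, QT in the shift-table sentence may be shorthand for both variables. The literal reading is not certain, but the ambiguity itself needs removing.
- The ECG safety assessment does not rest on these counts alone. The section also covers PR, QRS, ventricular rate, new qualitative abnormalities and investigator interpretation.
- The schedule limits exposure. Protocol section 4 puts the Cycle 1 Day 1 ECG before treatment, and 4.4.1 puts end of treatment 30 (±3) days after the last treatment visit. Later on-treatment ECGs arise only when clinically indicated.

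Reporting uncorrected QT beside QTc is not in itself an error. What stands is that the plan counts raw-QT flags that heart rate alone can produce, builds its one categorical table on a variable it calls QT, and leaves QTc undefined.

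**Conclusion.** The point holds in limited form and is of minor importance. Ordinary slowing of the heart can trigger the 30 ms flag on uncorrected QT, and larger slowing the 60 ms flag, with no change in QTc. Those flags would fall in the raw-QT counts, beside QTc counts that show no change if the correction fits. Read literally, the shift table places a QTc just above 500 ms in its lowest row at ordinary clinic rates, while the QTc listing and counts still capture it.

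The individual conversions are exact given Fridericia or Bazett. The 7% to 16% range depends on the assumed heart-rate model and indicates order of magnitude only. The output affected is a secondary descriptive safety table; the MTD determination and the PFS analysis do not use it.

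**What to change.** Amend SAP 8.4.5 to:

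1. Name one correction formula, for example Fridericia, and derive QTc centrally from the recorded QT and ventricular rate in place of machine- or site-reported values.
2. Apply the five notable limits to that QTc.
3. State that the categorical shift table uses the same QTc.
4. Report uncorrected QT descriptively and in listings, without flags.

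After the change, a patient with constant QTc 400 ms whose rate falls from 80 to 60 bpm shows a change of 0 ms instead of +37 to +54 ms. A patient with QTc 501 ms at 90 bpm (raw QT 438 ms by Fridericia or 409 ms by Bazett) moves from the lowest shift row to the highest.

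The cost is SAP wording and one derived variable, with no new data collection. The downside is that raw-QT outlier counts are no longer reported. If the sponsor wants to keep them, they should be labelled as uncorrected and shown apart from the QTc results.
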